### 6.1 Wrist Circumference Distribution of Study Subjects

- 1) At least 20% of the experimenters shall have the circumference within 1/4 of the entire limb circumference. (Minimum 17 subjects)
- 2) At least 10% of the experimenters shall have the circumference within top 1/8 of the entire limb circumference. (Minimum 9 subjects)
- 3) At least 10% of the experimenters shall have the circumference within lowest 1/8 of the entire limb circumference. (Minimum 9 subjects)

H2-BP shall take the wrist circumference as the criterion of measuring as it is a wrist band type and measures the pressure by wearing on the wrist. The wrist circumference is marked in centimeter. The minimum subjects in each sector are as follows as H2-BP is regulated for the people with 15-19cm wrist circumference to use the unit.

- 15.0–15.5625 cm: At least 10% (minimum 9 subjects)
- 15.5625–16.125 cm: At least 10% (minimum 9 subjects)
- 16.125–17.25 cm: At least 20% (minimum 17 subjects)
- 17.25–18.375 cm: At least 20% (minimum 17 subjects)
- 18.375–18.9375 cm: At least 10% (minimum 9 subjects)
- 18.9375–19.5 cm: At least 10% (minimum 9 subjects)

## 6.2 Age Constitution

Over 19

## 6.3 Gender Constitution of Study Subjects

Minimum respective 30% of female and male shall constitute entire subjects

## 6.4 Upper Arm Circumference Distribution of Study Subjects

- The bladder length of the comparator device should be 75–100% of the subject's upper arm circumference.
- The bladder width of the comparator device should be 37–50% of the subject's upper arm circumference.

# 7. Inclusion/Exclusion Criteria on Patients

## 7.1 Inclusion/Exclusion Criteria for Subjects of the Investigational Device

### 1) Inclusion Criteria

- (1) The out patients, hospitalized patients and applicants over 19 who show symptoms of hypotension, normal blood pressure, borderline hypertension and high blood pressure
- (2) Inclusion of subjects who meet the count of the targeted patient and rationale of estimation, i.e. wrist circumference, age, gender and circumference of the upper arm (Refer to section 6)
- (3) Inclusion of subjects who agreed in written form to decide the participation and comply the cautions after listening and understanding fully the details on this clinical study.

### 2) Exclusion Criteria

- (1) The subjects who disagreed to participate into this study
- (2) The subjects likely not to maintain the constant blood pressure about 30 minutes due to hypovolemia or quasi equivalent disease and situation
- (3) The subjects likely not to maintain the constant blood pressure about 30 minutes due to short-termly active vasoactive agonist or quasi equivalent medication
- (4) Subjects with cardiac arrhythmia
- (5) Subjects who ate food within 30 minutes
- (6) The subjects who took caffeine drink within 1 hour or smoked within 15 minutes
- (7) The subjects who made exercise immediately before measuring the blood pressure
- (8) Other subjects who are inappropriate to this study by the decision of the research staff

## 7.2 Inclusion/Exclusion Criteria for Users of the Investigational Medical Device

### 1) Inclusion Criteria

- (1) The subjects to be tested with the stethoscope type blood pressure gauge shall acquire appropriate hearing power and eyesight.
- (2) The subjects to be tested with the stethoscope type blood pressure gauge shall have training and experience on measuring.
- (3) The subjects who voluntarily agreed to sign after listening the explanation on the objective and procedure of the clinical study

### 2) Exclusion Criteria

- (1) The subjects who were decided as inappropriate for participating into the clinical study by the person in charge for the clinical study and other research staff

## 8. Information and Management of a Medical Instrument for Clinical Study

### 1) Investigational Device

- (1) Model: H2-BP
- (2) Product name(Product category No.) and class: Automatic electronic blood pressure gauge(A23010.04) / class II
- (3) Manufacturer: Charmcare Co., Ltd
- (4) Shape and structure  
-H: 81.5mm, L: 79.5mm, W: 25.5mm
- (5) Storage conditions: Store at room temperature

### 2) Comparator

- (1) Model: big ben® Sphygmomanometer
- (2) Product name(Product category No.) and class: Aneroid type blood pressure gauge(A23010.01) / class I
- (3) Manufacturer: Riester
- (4) Shape and structure  
-H: 250mm, L: 250mm, W: 250mm
- (5) Storage conditions: Store at room temperature

The investigational device used in this clinical trial is provided by Charmcare Co., Ltd. The Investigational Device Manager (hereinafter referred to as the "Manager") is responsible for the receipt, inventory management, application and use, and return of the investigational device. The Manager shall document all relevant activities and periodically report them to the Principal Investigator (PI).

In accordance with Good Clinical Practice for medical device clinical study, the Manager shall record the application period, lot number or serial number, expiration date (if applicable), Unique Device Identification, and Subject Identification Code for each subject using the investigational device.

The Manager and relevant personnel shall maintain and document medical records verifying the device is used in accordance with the clinical study protocol for each subject. The investigational site is responsible for ensuring that records related to medical device management are retained in compliance with applicable regulations and guidelines. The Principal Investigator is ultimately responsible for managing the investigational devices used in this study.

## 9. Study Design and Methodology

This clinical study is a single-arm, single-center, open-label, non-randomized, prospective, single-day study. The investigational device will be applied for blood pressure measurement in outpatients, inpatients, and volunteers aged 19 years or older who present with hypotension, normotension, borderline hypertension, or hypertension.

### 9.1 Implementation of Monitoring for Subjects Using the Investigational Device

For subjects undergoing monitoring (or their legally authorized representatives, if applicable), screening shall be conducted after obtaining written informed consent for participation in the clinical study. Based on the screening assessment, subjects who meet the inclusion criteria and do not meet the exclusion criteria will be enrolled in the study.

Blood pressure measurements will be performed in a seated position, alternating between the investigational device and the comparator device. The measurement procedure follows the steps below:

1. Using the comparator device, one valid pair of systolic and diastolic blood pressure (BP) values will be obtained from the upper arm as shown in Figure 1.
2. The investigational device will then be applied to the same arm's wrist, and one valid pair of systolic and diastolic BP values will be obtained.
3. Steps 1 and 2 will be repeated until three valid pairs of BP values are collected for each subject. A minimum interval of 60 seconds will be maintained between each measurement.
4. The same procedure will be followed for all other enrolled subjects.

[figure not shown]

Figure 1. ①Stethoscope ②Comparator Device Manometer ③Pump ④Investigational Device

The investigational device measurement is recorded by a single operator. In contrast, the comparator device measurement is recorded by two independent operators, each using a separate stethoscope to simultaneously assess and document the blood pressure readings.

When measuring diastolic blood pressure (DBP) using auscultation, Korotkoff Phase V should be recorded. If Korotkoff Phase V is not audible, the subject shall be excluded from the study.

The two operators using the auscultatory blood pressure measurement method must conduct their measurements independently, ensuring that they cannot communicate or be aware of each other's recorded values for each subject. Additionally, during the measurement process, the operators must not have access to the investigational device's readings.

\* If the difference between the two simultaneous measurements exceeds the following thresholds, the corresponding blood pressure value pair shall be excluded:

- If the systolic blood pressure (SBP) difference between the two operators is greater than 4 mmHg, the value pair is excluded.
- If the diastolic blood pressure (DBP) difference between the two operators is greater than 4 mmHg, the value pair is excluded.

To ensure validity and representativeness of the blood pressure measurements, the final collected values from the comparator device must meet the following distribution criteria:

- 1) At least 5% of SBP values should be  $\leq 100$  mmHg.
- 2) At least 5% of SBP values should be  $\geq 160$  mmHg.
- 3) At least 20% of SBP values should be  $\geq 140$  mmHg.
- 4) At least 5% of DBP values should be  $\leq 60$  mmHg.
- 5) At least 5% of DBP values should be  $\geq 100$  mmHg.
- 6) At least 20% of DBP values should be  $\geq 85$  mmHg.

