	
2. Inclusion/Exclusion Criteria for Users of the Investigational Device
 
1) Inclusion Criteria
 
(1) The subjects to be tested with the stethoscope type blood pressure gauge shall acquire appropriate hearing power and eyesight.
 
(2) The subjects to be tested with the stethoscope type blood pressure gauge shall have training and experience on measuring.
 
(3) The subjects who voluntarily agreed to sign after listening the explanation on the objective and procedure of the clinical study
 
2) Exclusion Criteria
 
The subjects who were decided as inappropriate for participating into the clinical study by the person in charge for the clinical study and other research staff

Clinical study Period	About 23 months - Study Protocol and IRB Approval: approximately 2 months - Study Contract and Administrative Procedures Execution: approximately 1month - Subject Recruitment and Study Procedure Execution: approximately 19 months - Analyze data and report results: approximately 1 month
Investigational Device	
1. Investigational Device
 
1) Model: H2-BP 2) Product name(Product category No.) and class: Automatic electronic blood pressure gauge(A23010.04)/Class II 3) Manufacturer: Charmcare Co., Ltd 4) Shape and structure: -H: 81.5mm, L: 79.5mm, W: 25.5mm 5) Storage conditions: Store at room temperature
 
2. Comparator
 
1) Model: big ben® Sphygmomanometer 2) Product name(Product category No.) and class: Aneroid type blood pressure gauge(A23010.01) / class I 3) Manufacturer: Riester 4) Shape and structure: - H: 250mm, L: 250mm, W: 250mm 5) Storage conditions: Store at room temperature

Instructions for use	The Investigational Device will be applied to one wrist of the patient to measure blood pressure, followed by the application of the comparator to the upper arm of the same arm to measure blood pressure. The procedure for use

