## 6. Planned Sample Size

Planned Sample Size: 141 Subjects (Minimum Enrollment: 85 Subjects)

Rationale for Sample Size Calculation: According to the guidelines outlined in ISO 81060-2 Third Edition 2018-11 (Non-invasive sphygmomanometers - Part 2: Clinical investigation of intermittent automated measurement type [including: Amendment 1 (2020)]) and EN 1060-4 (Non-invasive sphygmomanometers - Part 4: Test procedures to determine the overall system accuracy of automated non-invasive sphygmomanometers), a minimum of 85 subjects must be enrolled to evaluate the accuracy of electronic sphygmomanometers.

Considering potential data loss due to withdrawal of consent and other unforeseen circumstances, an anticipated dropout rate of approximately 40% has been applied. Accordingly, a total of 141 subjects will be recruited for this study.

Composition of Study Subjects: In accordance with the ISO 81060-2 Third Edition 2018-11 international standard for the clinical validation of electronic sphygmomanometers, the enrolled subjects must meet the following composition criteria.

The investigator is responsible for continuous monitoring of subject enrollment status to ensure compliance with the required composition. If the composition criteria are not met, additional subjects may be recruited as necessary to fulfill the requirements.

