## 11. Effectiveness Evaluation Parameter

Evaluate the accuracy by adopting the following evaluation parameters by measuring the blood pressure in three times at systolic and diastolic area from total 141 subjects. The qualification decision shall be pursuant to the following criteria. (The minimum subjects shall be over 85 and measured data shall be over 255 cases.)

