### 11.1 Primary Endpoint

(1) Average on difference between blood pressures measured with investigational device and comparator

n=Count of measurement Ex) For 85 subjects-> n=255

i is a separate index for count of measurement.

$$p_{\text{comparator-}sq_i} = \frac{1}{4} \times (p_{\text{comparator}_{i,1}} + p_{\text{comparator}_{i,2}} + p_{\text{comparator}_{i+1,1}} + p_{\text{comparator}_{i+1,2}})$$

$p_{\text{comparator}_{i,1}}$  is the blood pressure data measured at i – th time by the operator 1

$p_{\text{comparator}_{i,2}}$  is the blood pressure data measured at i – th time by the operator 2

[Formula for calculating the primary endpoint]

$$\text{Average of difference}(\bar{x}_n) = \frac{1}{n} \times \sum_{i=1}^n (p_{\text{Investigational device}_i} - p_{\text{comparator-}sq_i})$$

Corresponding endpoint shall have error range less than  $\pm 0.67$  kPa.

(2) Standard deviation on the blood pressures measured with investigational device and comparator. (Based on count of measurement)

n= Count of measurement Ex) For 85 subjects -> n=255

i is a separate index for count of measurement.

[Formula for calculating the primary endpoint]

$$\text{Standard deviation of difference based on count of the measurements} (s_n) = \sqrt{\frac{1}{n-1} \times \sum_{i=1}^n (x_i - \bar{x}_n)^2}$$

Corresponding endpoint shall have error range less than 1.07 kPa.

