## 11.2 Secondary Endpoint

(1) Standard deviation on difference between blood pressures measured with investigational device and comparator. (Based on the count of the subjects)

m= Count of measurement Ex) For 85 subjects -> n=255

j is a separate index for count of measurement.

d is the count of measurement per experimentee.

k is an index for the individual factor.

$$x_j = \frac{1}{d} \times \sum_{k=1}^d (p_{\text{investigational device}_{j,k}} - p_{\text{comparator-}sq_{j,k}})$$

$$p_{\text{comparator-}sq_{j,k}} = \frac{1}{4} \times (p_{\text{comparator}_{j,k,1}} + p_{\text{comparator}_{j,k,2}} + p_{\text{comparator}_{j,k+1,1}} + p_{\text{comparator}_{j,k+1,2}})$$

[Formula for calculating the secondary endpoint]

$$\text{Standard deviation of difference based on count of the subjects} (s_m) = \sqrt{\frac{1}{m-1} \times \sum_{j=1}^m (x_j - \bar{x}_n)^2}$$

The secondary endpoint shall meet the Table 1 or 2 based on ISO 81060-2 standard depending on the blood pressure data.

Table 1 – Average subject data acceptance (criterion 2) in mmHg

$\bar{x}_n$	Maximum permissible standard deviation, $s_m$ , as function of, $\bar{x}_n$ mmHg									
	0,0	0,1	0,2	0,3	0,4	0,5	0,6	0,7	0,8	0,9
$\pm 0,$	6,95	6,95	6,95	6,95	6,93	6,92	6,91	6,90	6,89	6,88
$\pm 1,$	6,87	6,86	6,84	6,82	6,80	6,78	6,76	6,73	6,71	6,68
$\pm 2,$	6,65	6,62	6,58	6,55	6,51	6,47	6,43	6,39	6,34	6,30
$\pm 3,$	6,25	6,20	6,14	6,09	6,03	5,97	5,89	5,83	5,77	5,70
$\pm 4,$	5,64	5,56	5,49	5,41	5,33	5,25	5,16	5,08	5,01	4,90
$\pm 5,$	4,79	-	-	-	-	-	-	-	-	-

Example For mean of  $\pm 4,2$ mmHg the maximum permissible standard deviation is 5,49 mmHg.

Table 2 – Average subject data acceptance (criterion 2) in kPa

$\bar{x}_n$	Maximum permissible standard deviation, $s_m$ , as function of, $\bar{x}_n$ kPa									
	0,000	0,010	0,020	0,030	0,040	0,050	0,060	0,070	0,080	0,090
$\pm 0,0$	0,9266	0,9266	0,9266	0,9266	0,9226	0,9246	0,9233	0,9223	0,9213	0,9203
$\pm 0,1$	0,9193	0,9183	0,9173	0,9163	0,9152	0,9138	0,9119	0,9099	0,9079	0,9059
$\pm 0,2$	0,9039	0,9007	0,8989	0,8970	0,8946	0,8906	0,8878	0,8855	0,8826	0,8785
$\pm 0,3$	0,8756	0,8723	0,8679	0,8641	0,8601	0,8562	0,8519	0,8471	0,8414	0,8374
$\pm 0,4$	0,8333	0,8283	0,8226	0,8169	0,8119	0,8059	0,7999	0,7933	0,7853	0,7793
$\pm 0,5$	0,7739	0,7669	0,7599	0,7531	0,7463	0,7388	0,7319	0,7237	0,7157	0,7077
$\pm 0,6$	0,6999	0,6891	0,6802	0,6723	0,6670	0,6595	0,6488	0,6386	-	-

Example For mean of  $\pm 0,520$ kPa the maximum permissible standard deviation is 0,7599 kPa.

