### (c) Handling of Missing Data

If missing data occur due to dropout or other reasons, no imputation is performed. Analyses will be conducted only on the collected data.

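### The reference formula needs four comparator readings per subject, but section 9.1 takes three and ends on the device, so every subject's third difference has no defined reference

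*Combined protocol and SAP*

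**What the plan says.** Section 9.1 sets a two-step cycle: step 1 is the comparator on the upper arm, step 2 the investigational device on the same wrist. "Steps 1 and 2 will be repeated until three valid pairs of BP values are collected for each subject", with at least 60 seconds between measurements.

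Section 11.1 defines the reference for measurement i as the mean of four values: operators 1 and 2 at comparator reading i, and the same two operators at comparator reading i+1. It says "i is a separate index for count of measurement" and "n=Count of measurement Ex) For 85 subjects-> n=255", and does not mention subjects in the index. Section 11.2 uses the same construction within subject j, with readings k and k+1, and averages the differences over d, where "d is the count of measurement per experimentee".

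Section 11 adds a minimum: "The minimum subjects shall be over 85 and measured data shall be over 255 cases". Section 15.1(c) says that for missing data "no imputation is performed. Analyses will be conducted only on the collected data".

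The Summary (Instructions for use) gives the opposite order: "The Investigational Device will be applied to one wrist of the patient to measure blood pressure, followed by the application of the comparator". Its Test method entry says only that the two instruments alternate, and caps a subject at eight attempts without saying what counts as one.

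**The concern.** The formula is meant for a device reading that sits between two comparator readings. Three device readings used this way need four comparator readings, and the cycle in section 9.1 provides three. Repeating a cycle after an invalid pair does not close the gap, because every cycle ends on the device.

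Both primary criteria (mean difference within ±0.67 kPa, standard deviation below 1.07 kPa) and the secondary standard deviation are built on this reference. If the plan is followed exactly, someone must decide after the data are in whether to drop the third reading, reference it to the third comparator reading alone, or use a reading from another subject. Each choice can give a different mean, standard deviation and number of differences in a pass/fail assessment.

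**Working it through.** **Inputs.** Three device readings per subject (section 11, and 255/85 = 3 from section 11.1); the order in section 9.1, steps 1 to 3; the reference formula in sections 11.1 and 11.2; 85 subjects minimum, 141 planned and about 40% loss (section 6).

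**The plan's own figure.** 85 × 3 = 255, as stated. So all three device readings per subject are meant to enter the analysis.

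**Which references exist.** Write R for a comparator reading and T for a device reading. The formula is ref(T_k) = ¼ × (R_k,1 + R_k,2 + R_k+1,1 + R_k+1,2), where the second subscript is the operator.

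| Device reading | Needs | Section 9.1: R1 T1 R2 T2 R3 T3 | Summary: T1 R1 T2 R2 T3 R3 | Section 9.1 plus closing R4 |
|---|---|---|---|---|
| T1 | R1, R2 | both taken, one on each side | both taken, both after T1 | both taken, one on each side |
| T2 | R2, R3 | both taken, one on each side | both taken, both after T2 | both taken, one on each side |
| T3 | R3, R4 | R4 not taken | R4 not taken | both taken, one on each side |

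**Computable differences with the reference kept within the subject.**
- 85 subjects: 2 × 85 = 170 of 255; 85 undefined (33.3%).
- 141 subjects: 2 × 141 = 282 of 423; 141 undefined (33.3%).
- In section 11.2 with d = 3, the third term of the subject mean x_j is undefined for every subject.

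**The 255-case minimum.**
- If it counts computable differences: 2 × 127 = 254 and 2 × 128 = 256, so 128 completers are needed. From 141, at most 141 − 128 = 13 may be lost (13/141 = 9.2%). Section 6 says "an anticipated dropout rate of approximately 40% has been applied"; 141 × 0.60 = 84.6, so about 85 completers and 170 differences.
- If it counts device readings: 3 × 85 = 255, and 85 subjects reach it.

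**Section 11.1 read literally, with i running from 1 to 255 across subjects.** A subject boundary falls at i = 3, 6, …, 252, which is 84 places. At each, reading i+1 is the next subject's first comparator reading. At i = 255 the formula calls for reading 256, which does not exist.

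As an illustration of what the borrowing would do, assume consecutive subjects are unrelated, with a between-subject systolic SD s of 15 to 25 mmHg (an assumption; the documents give no SD). An affected reference is off by half the difference between two subjects, which has variance 2s²/4 = s²/2. Spread over all differences, one third of which are affected, this is s²/6. The added SD is s/√6: 15/2.449 = 6.1 mmHg to 25/2.449 = 10.2 mmHg. The limit of 1.07 kPa is about 8.0 mmHg, using the ratio of the first entries of Tables 1 and 2 in section 11.2 (6.95/0.9266 = 7.50; 1.07 × 7.50 = 8.0).

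**The case against.** The strongest reply is that the term valid pair is never defined across the two instruments. If it means a device reading together with its complete reference, collecting three pairs already implies a fourth comparator reading, and a cap of eight attempts has room for it. But the steps of section 9.1 use the term for the systolic and diastolic values from one instrument. A cap is a ceiling and schedules nothing. Repeating steps 1 and 2 in full to obtain R4 would also take eight inflations, the whole cap if inflations are what it counts.

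Several narrower points stand, at least in part:
- The one-third figure for the primary endpoint takes the within-subject index from section 11.2. Read literally, section 11.1 leaves only the last difference without a reference, but then 84 others use the wrong subject's pressure.
- The missing-data rule may not have been written for a reading that was never scheduled. If it applies, it points to two differences per subject, which contradicts the plan's example of 255 for 85 subjects.
- The shortfall against the 255 minimum depends on what is counted; counting device readings is a natural interpretation.
- Under the Summary's order no device reading is bracketed if the labels k and k+1 are taken as written. By position, T2 and T3 would lie between comparator readings and T1 would not.
- No effect on the pass/fail result has been shown. The case rests on an undefined quantity, not on a demonstrated bias.

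**Conclusion.** The point holds and must be fixed. With the order in section 9.1 and the formula in section 11.2, one of every three differences has no defined reference: 85 of 255 at the minimum size, 141 of 423 at the planned size. The literal alternative in section 11.1 mixes subjects and still fails on the last term. This affects both primary criteria and the secondary standard deviation, for systolic and diastolic pressure. The counts assume that a pair in section 9.1 means the values from one instrument and that the reference is meant to stay within the subject, as the indices in section 11.2 show. They need no assumption about variability or drift. The 128-completer threshold applies only if the minimum in section 11 counts computable differences.

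**What to change.** Reconcile the Summary and sections 9.1, 11.1 and 11.2 to one sequence that matches the formula: comparator, device, comparator, device, comparator, device, comparator. Write section 11.1 with the indices of section 11.2 (subject j; device readings k = 1 to 3; comparator readings 1 to 4), so that the next reading can never belong to another subject.

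If no closing reading is added, prespecify in sections 11.1 and 11.2 that the third device reading is referenced to that subject's own third comparator reading only. State that this difference is unbracketed and rests on two operator values instead of four. For any subject already measured without a closing reading, this is the only one of the two options left.

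State also whether the 255 minimum counts device readings or computable differences. Once either remedy is in place the two agree at three per completing subject, so this is a clarification.

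The cost is protocol wording plus one cuff reading of a minute or two per subject. Seven readings have six intervals of 60 seconds, at least 6 minutes of waiting, within the 10 to 30 minutes in the Summary. Comparator readings rise from 3 × 85 = 255 to 4 × 85 = 340 at 85 subjects, and from 423 to 564 at 141. Two consequences need a sentence each:
- If each inflation counts towards the cap of eight, one spare attempt remains (8 − 7) instead of two (8 − 6).
- The section 13 rule that excludes a subject when any pair of reference readings differs too much would cover 6 possible pairs instead of 3, so it could exclude more subjects.

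The formula-only option needs no extra reading, but for one third of the differences it gives up bracketing and half the reference values.
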